## 5.2 Secondary Efficacy Endpoints

The following secondary efficacy endpoints, as derived from the e-diary, are the change from baseline to weeks 4, 8 and 12 in:

- Mean number of micturitions per 24 hours (only week 4 and week 8)
- Mean number of urgency episodes per 24 hours
- Mean number of daytime incontinence episodes per 24 hours
- Mean number of nighttime incontinence episodes per 24 hours
- Mean number of urge incontinence episodes per 24 hours
- OABSS, the sum score of four symptoms (daytime frequency, nighttime frequency, urgency, and urge incontinence)

### 5.2.1 Mean Number of Micturitions per 24 hours (Week 4 and Week 8)

Derivation of the endpoint is the same described in Section 5.1.

Change from baseline to visit 3/week 4 is defined as: Result at visit 3/week 4 – Result at baseline (visit 2/week 0).

Change from baseline to visit 4/week 8 is defined as: Result at visit 4/week 8 – Result at baseline (visit 2/week 0).

### 5.2.2 Mean Number of Urgency Episodes per 24 hours

Mean number of urgency episodes per 24 hours (see definition in Table 1) is derived from "PPIUS-Urgency of the Micturition" from Bladder Diary.

Scoring PPIUS scale:

- Grade 0: No urgency I felt no need to empty my bladder, but did so for other reasons
- Grade 1: Mild urgency I could postpone voiding as long as necessary, without fear of wetting myself
- Grade 2: Moderate urgency I could postpone voiding for a short while, without fear of wetting myself
- Grade 3: Severe urgency I could not postpone voiding, but had to rush to the toilet in order not to wet myself
- Grade 4: Urge incontinence I leaked before reaching the toilet

Let  $N_{34}$  equal the number of times that a subject recorded a grade 3 or 4 urgency episode on a diary day. If there are no valid diary days, then  $N_{34}$  is missing, while if there are no grade 3 or 4 urgency episodes on a valid diary day, then  $N_{34}$  equals 0.

For each subject, the mean number of grade 3 or 4 urgency episodes per 24 hours, at Visit x (x=2, 3, 4 and 5), is the mean of N34 over the valid diary days of the Episodic Diary.

Sum of the number of grade 3 – 4 urgency episodes (per 24 hrs) over the valid diary days prior to Visit x Number of valid diary days

### 5.2.3 Mean Number of Daytime and Nighttime Incontinence Episodes per 24 hours

Number of Incontinence Episodes per 24 hours will be derived from "Number of Incontinence Episodes During the Day" and "Number of Incontinence Episodes During the Night" collected in the Bladder Diary: responses "Pee in toilet and Leakage" and "Leakage". The number of incontinence episodes during the day includes the episodes from the time when subject wakes up until the time the subject sleeps. The number of incontinence episodes the episodes from the time the subject sleeps till the next morning wake up time, see Table 2.

For each subject, the mean number of incontinence episodes per day/night (during the day/night) at Visit x (x=2, 3, 4 and 5) will be calculated using all available number of incontinence episodes for the valid diary days in the Diary for daytime and for nighttime:

Mean Number of Daytime Incontinence Episodes at Visit x = Total number of "Daytime Leakage Counts" over the Valid Diary Days prior to Visit x Number of Valid Diary Days

Mean Number of Nighttime Incontinence Episodes at Visit x = Total number of "Nighttime Leakage Counts" over the Valid Diary Days prior to Visit x Number of Valid Diary Days

## 5.2.4 Mean Number of Urge Incontinence Episodes per 24 hour

Number of urge incontinence episodes per 24 hours will be derived from the Bladder Diary: responses "Pee in toilet and Leakage", "Leakage" and a PPIUS score of 3 or 4.

For each subject, the mean number of urge incontinence episodes at Visit x (x=2, 3, 4 and 5), using all available incontinence periods and PPIUS scores for the valid days in the diary, will be calculated as:

Sum of the number of urge ncontinence episodes (per 24 hrs) over the valid diary days prior to Visit x Number of valid diary days

#### 5.2.5 Overactive Bladder Symptom Score (OABSS)

Baseline for OABSS is defined as the day the subject visits the clinic for visit 2.

The OABSS questionnaire is designed to quantify OAB symptoms as a single score, and contains questions that address 4 symptoms of overactive bladder:

- Daytime frequency,
- Nighttime frequency,
- Urgency,
- Urge incontinence.

The OABSS is composed of 4 questions (one per each symptom) and has a minimum score of 0 and a maximum score of 15. If a subject experiences a more urgent episode the corresponding urgency score is higher and, consequently, the total score will be higher (see [Section 10.7 Appendix 7 Overactive Bladder Symptom Score questionnaire in the protocol]). If one or more of the 4 questions are not answered in the eDiary then the OABSS will be set to missing.

Questionnaires to be completed by the subject at the site in the local language and provided via the e-diary. In case the subject forgets to bring the device, then a back-up device will be used. Results will be directly entered in the e-diary by the subject.

#### 5.2.6 Efficacy Endpoints for the Mirabegron 25 mg Starting Dose

The following efficacy endpoints for the Mirabegron 25 mg starting dose will be evaluated with descriptive statistics:

- Change from baseline to weeks 4, 8, and 12 in mean number of micturition/24 hours;
- Change from baseline to weeks 4, 8, and 12 in mean number of grade 3 or 4 (PPIUS) urgency episodes;
- Change from baseline to weeks 4, 8, and 12 in mean number of incontinence episodes;
- Change from baseline to weeks 4, 8, and 12 in urge incontinence episodes/24 hours;
- Change from baseline to weeks 4, 8, and 12 in OABSS.

## **5.3 Exploratory Endpoints**

There are no exploratory endpoints.

# 5.4 Safety Endpoints

Safety data will be summarized for both treatment groups ('Mirabegron 50 mg' and 'Mirabegron 25 mg') and visit, unless otherwise specified. Safety data will be assessed by evaluation of the following variables:

- Treatment-emergent adverse events (TEAEs; frequency, severity, seriousness, and relationship to study drug).
- Clinical laboratory variables (hematology, biochemistry including liver enzymes and total bilirubin, and urinalysis)
- Vital signs (systolic and diastolic blood pressure, pulse rate and body temperature)
- 12-lead electrocardiogram (ECG)
- Post Void Residual Volume (PVR)

The following sequence order will be in effect when more than 1 assessment is required at a time point: routine 12-lead ECG, vital signs, and samples for safety laboratories.

### 5.4.1 Adverse Events

AEs will be coded using MedDRA. A TEAE is defined as an AE observed after starting administration of the IP until 30 days after the final administration of IP. If the adverse event occurs on Day 1 and the onset check box on the (AE) eCRF is marked "Onset after first dose of study drug" or the onset check box is left blank, then the adverse event will be considered treatment emergent. If the adverse event occurs on Day 1 and the onset check box is marked "Onset before first dose of study drug", then the adverse event will not be considered treatment emergent. If a subject experiences an event both during the pre-investigational period and during the investigational period, the event will be considered as TEAE only if it has worsened in severity (i.e., it is reported with a new start date).

A drug-related TEAE is defined as any TEAE with at least possible relationship to study treatment as assessed by the investigator or with missing assessment of the causal relationship.

AEs may be upgraded by the sponsor according to the Important Medical Event process.

A drug-related TEAE is defined as any TEAE with at least a possible relationship to study treatment as assessed by the investigator or with a missing assessment of the causal relationship.

Common TEAEs are defined as preferred terms (PTs) that have been reported by at least 5% of the subjects, in any treatment group.

When an AE start or stop date is missing, the date will be imputed using the rules in Section 6.10.2.2.

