7.3 Adverse Events and Other Safety Aspects

The definitions of an AE or SAE can be found in [Sections 10.3.1 Definition of Adverse Events and 10.3.2 Definition of Serious Adverse Events], respectively.

AEs will be reported by the subject.

The investigator and any qualified designees are responsible for detecting, documenting and recording events that meet the definition of an AE or SAE and remain responsible for following up AEs that are serious, considered related to the study IP, or that caused the subject to discontinue the IP and/or study [Section 10.3 Appendix 3 Adverse Events: Definitions and Procedures for Recording, Evaluating, Follow-up and Reporting].

The method of recording, evaluating, and assessing causality of AE and SAE and the procedures for completing and transmitting SAE reports are provided in [Section 10.3 Appendix 3 Adverse Events: Definitions and Procedures for Recording, Evaluating, Follow-up and Reporting].

7.3.1 Time Period and Frequency for Collecting Adverse Event and Serious Adverse Event Information

All SAEs will be collected from the signing of the ICF until 30 days after the final IP administration or when the subject is determined to be a screen failure and reported in the eCRF.

All AEs will be collected from the signing of the ICF until 30 days after the final IP administration or when the subject is determined to be a screen failure and reported in the eCRF.

If the severity of an SAE/AE changes, the event should be relisted in the eCRF with the new severity and new onset date.

If the severity decreases, the SAE/AE should be relisted in the eCRF with the new severity and new onset date. The exception is ongoing pre-dose events that continue post-dose and improve post-dose. Such events should not be re-listed.

If the severity of an SAE reduces, the details of the AE should be provided on the SAE worksheet for the medical assessor to be able to assess the course of the event.

All SAEs will be recorded and reported to the sponsor or designee immediately and under no circumstance should this exceed 24 hours, as indicated in [Section 10.3 Appendix 3 Adverse Events: Definitions and Procedures for Recording, Evaluating, Follow-up and Reporting]. The investigator will submit any updated SAE data to the sponsor within 24 hours of it being available.

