9.4.3.1 Adverse Events

AEs will be coded using MedDRA. A TEAE is defined as an AE observed after starting administration of the IP and 30 days after the final administration of IP. An IP-related TEAE is defined as any TEAE with a causal relationship assessed as "yes" by the investigator.

The number and percentage of subjects with TEAEs, drug-related TEAEs, serious TEAEs, drug-related serious TEAEs, TEAEs leading to leading to withdrawal of treatment and drug-related TEAEs leading to leading to withdrawal of treatment as well as TEAEs of special interest [Section 7.3.6 Adverse Events of Special Interest] will be summarized by SOC, preferred term and treatment group. The number and percentage of TEAEs by severity will also be summarized. The worst severity will be summarized if the same AE is recorded more than once for a subject.

AE data will be listed.

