10.3.1 Definition of Adverse Events

AE Definition:

An AE is any untoward medical occurrence in a patient or clinical study subject, temporally associated with the use of study IP whether or not considered related to the study IP.

"Adverse event" means any untoward medical occurrence associated with the use of a drug in humans, whether or not considered drug related.

NOTE: An AE can therefore be any unfavorable and unintended sign (including an abnormal laboratory finding), symptom, or disease (new or exacerbated) temporally associated with the use of study IP. This includes events related to the comparator and events related to the (study) procedures.

Events Meeting the AE Definition

- Any abnormal laboratory test results (hematology, clinical chemistry, or urinalysis) or other safety assessments (e.g., ECG, radiological scans, vital signs measurements), including those that worsen from baseline, considered clinically significant in the medical and scientific judgment of the investigator (i.e., not related to progression of underlying disease)
- Exacerbation of a chronic or intermittent pre-existing condition including either an increase in frequency and/or intensity of the condition
- New conditions detected or diagnosed after study IP administration even though it may have been present before the start of the study

Events NOT Meeting the AE Definition

- Any clinically significant abnormal laboratory findings or other abnormal safety assessments which are associated with the underlying disease, unless judged by the investigator to be more severe than expected for the subject's condition
- The disease/disorder being studied or expected progression, signs, or symptoms of the disease/disorder being studied, unless more severe than expected for the subject's condition
- Medical or surgical procedure (e.g., endoscopy, appendectomy): the condition that leads to the procedure is the AE
- Situations in which an untoward medical occurrence did not occur (social and/or convenience admission to a hospital)
- Anticipated day-to-day fluctuations of pre-existing disease(s) or condition(s) present or detected at the start of the study that do not worsen

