Subject	An individual in the population of interest who participates in a clinical trial as recipient of the investigational product.	
Treatment emergent adverse event	An adverse event observed after starting administration of the study drug.	

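### SAP 5.4.1 gives two non-equivalent tests for an event seen both before and after first dose, so TEAE counts depend on which one is programmed

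*SAP*

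**What the plan says.** Three places define a TEAE by timing alone.

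- Protocol 9.4.3.1: "A TEAE is defined as an AE observed after starting administration of the IP and 30 days after the final administration of IP".
- The opening of SAP 5.4.1: "A TEAE is defined as an AE observed after starting administration of the IP until 30 days after the final administration of IP".
- The SAP List of Key Terms: "An adverse event observed after starting administration of the study drug".

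Later in the same paragraph, SAP 5.4.1 adds a rule for a subject who has an event in the investigational period and also in the pre-investigational one: "the event will be considered as TEAE only if it has worsened in severity (i.e., it is reported with a new start date".

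Three recording rules in the protocol bear on how that sentence works.

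- Protocol 7.3.1 starts AE collection at consent: "All AEs will be collected from the signing of the ICF until 30 days after the final IP administration". Pre-dose AEs will therefore be in the database.
- Protocol 7.3.1 also says that when severity changes, "the event should be relisted in the eCRF with the new severity and new onset date". It then carves out one case: "The exception is ongoing pre-dose events that continue post-dose and improve post-dose". Such events are not relisted.
- Protocol 10.3.1 counts as an AE: "Exacerbation of a chronic or intermittent pre-existing condition including either an increase in frequency and/or intensity of the condition".

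The AE overview and the SOC/PT tables in SAP 6.5.1 are built on TEAEs. The AE listing in the same section covers AEs in the safety set and is not limited to TEAEs.

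**The concern.** The added sentence states a condition (worse severity) and then offers a different condition (a new start date) as its equivalent. They agree for an event that runs across the first dose. They disagree for an event that ended before dosing and came back on treatment without being more severe. Two programmers could each follow the SAP and produce different TEAE tables.

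Incidence and severity of AEs is a secondary endpoint, and the study is meant to support safety surveillance for the licence renewal. A classification rule that lowers TEAE counts under one of its readings, and that departs from the protocol under that reading, should be settled before the tables are produced.

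**Working it through.** The plan states no figure on this point, so there is none to reproduce. The check is to run each kind of event through the three rules.

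| Event | Protocol 9.4.3.1 (timing) | SAP 5.4.1, severity test | SAP 5.4.1, start-date test |
|---|---|---|---|
| (a) Continues across first dose, then worsens; relisted under Protocol 7.3.1 | TEAE | TEAE | TEAE |
| (b) Continues across first dose, then improves; not relisted | Unclear (observed on drug, but began earlier) | Not a TEAE | Not a TEAE |
| (c) Resolved before dosing, recurs on drug at higher severity | TEAE | TEAE | TEAE |
| (d) Resolved before dosing, recurs on drug at same or lower severity | TEAE | **Not a TEAE** | **TEAE** |
| (e) Pre-existing condition more frequent at same severity, entered as a new on-treatment AE | TEAE | **Not a TEAE** | **TEAE** |
| (f) Ongoing pre-dose AE more frequent at same severity, not relisted | AE seen on drug | Not a TEAE | Not a TEAE |

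Row (e) assumes that the earlier condition counts as the same event under the SAP sentence.

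**Where the two halves agree.** In (a) and (b) the start-date test works because of the relisting rule. A continuing event that worsens gets a new onset date; a continuing pre-dose event that improves does not.

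**Where they part.** Take a mild event from Day -8 to Day -6, and the same mild event with onset on Day 20. The second record has an on-treatment start date and is no more severe. The protocol gives 1 TEAE, the start-date test 1, and the severity test 0.

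**Direction.** Every event that worsens after dosing has a new on-treatment start date, by relisting in (a) or by recurrence in (c). So whatever passes the severity test also passes the start-date test. Rows (d) and (e) show that the converse fails. The severity reading can therefore only give the same count or a lower one.

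**Size.** The number of affected events is (subjects with a pre-dose AE) × (share whose event recurs on drug without worsening). The documents give neither term, so the product cannot be computed.

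For scale only, SAP 5.4.1 calls a preferred term common at 5% of subjects in any treatment group. The planned 249 subjects at 2:1 give 249 × 2/3 = 166 and 249 × 1/3 = 83. If all are treated:

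- 50 mg: 0.05 × 166 = 8.3, so 9 subjects reach the threshold.
- 25 mg: 0.05 × 83 = 4.15, so 5 subjects reach it.

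One reclassified subject could move a term across the line.

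**The case against.** The strongest reply is that the bracket is the operational test. Read with Protocol 7.3.1, the sentence is about one event spanning the first dose, and a new start date is how the database signals that it worsened. A recurrence entered as a fresh record has a new start date and would count, as it also would under the paragraph's opening definition. This reading is coherent. It shows that loss of recurrences is not established. It does not remove the conflict, because the sentence speaks of an event experienced in both periods, which covers a resolved and recurrent event, and its main clause makes worse severity a necessary condition.

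A second reply is that the protocol definition needs some supplement. It turns on when an event is observed, not on its onset, and taken literally it could sweep in pre-dose events that merely continue unchanged. That is fair: the SAP needs a rule for continuing events. It does not need one that can also exclude recurrences.

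A reader might go further than the documents allow in three ways.

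- **That recurrences vanish from every TEAE table.** This follows only if the severity half is programmed. Either way the events remain in the AE listing.
- **That frequency-only worsening is always lost.** Row (e) counts under the start-date test. Row (f) fails both tests, but mainly because Protocol 7.3.1 relists only on a change of severity. That is a recording gap, which SAP wording alone cannot close.
- **That counts of events of special interest must fall.** SAP 6.5.1 tabulates events of interest by preferred term without expressly limiting them to TEAEs. Protocol 9.4.3.1 does refer to TEAEs of special interest, so an effect would arise only where that restriction is applied.

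**Conclusion.** The concern holds as an inconsistency within one SAP sentence. For an event that resolved before dosing and recurs on drug at the same or lower severity, the severity test contradicts the timing-only definition in Protocol 9.4.3.1 and the SAP key terms, while the start-date test agrees with it. The SAP does not say which half governs. The direction is known: the severity reading can only lower TEAE counts. The size is not known.

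The conclusion rests on two assumptions: sites record a recurrence after resolution as a separate AE with its own onset date, and the pre-investigational period means the time from consent to first dose, with screening of about 1 to 2 weeks. That term is not among the key terms of either document. If it were taken to include medical-history conditions, the rule would reach more events. On the narrower reading the number of subjects affected is probably small.

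The change log in SAP 7.1 says that the TEAE definition was corrected to agree with the protocol. The replacement below would carry out that intent.

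**What to change.** Replace the sentence in SAP 5.4.1 with:

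> Any AE record with onset after first dose and up to 30 days after last dose, including recurrence of an event that had resolved before first dose, is a TEAE regardless of severity. A pre-dose event that continues across first dose is a TEAE only if it worsens and is therefore relisted with a post-dose onset date (Protocol 7.3.1).

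This keeps the link to the relisting rule where that link works and removes the undefined period name. The existing Day 1 check-box rule can stay, to decide whether a Day 1 onset falls before or after first dose. A rise in frequency recorded as a new on-treatment AE under Protocol 10.3.1 counts under the first sentence. An ongoing pre-dose AE that becomes more frequent and is not relisted remains outside; catching it would need a recording instruction to sites.

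The cost is one passage of SAP text and one derivation flag, with no new data. SAP section 1 allows revision before hard lock. The downside is that a few more recurrent background events will be counted as TEAEs.

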#### Adverse Events of Special Interest

Adverse Events of Special Interest include:

- Increased heart rate and tachycardia
- Increased blood pressure

- Hypersensitivity reactions
- Urinary retention
- QT prolongation

AEs of interest will be identified using all Preferred Terms (PT) from Standardized MedDRA queries (SMQ), version 23.0 or higher, see Table 3, or sponsor-defined list of search terms, see Appendix 9.3 AEs of Interest not covered by Standard MedDRA SMQs v23.0.

Table 3Standardized MedDRA Queries and PTs

CV - Increased blood pressure	Hypertension SMQ – Narrow search	
CV - Increased heart rate and tachycardia	Arrhythmia supraventricular (PT)	
	Atrial tachycardia (PT)	
	Heart rate abnormal (PT)	
	Heart rate increased (PT)	
	Rebound tachycardia (PT)	
	Sinus tachycardia (PT)	
	Supraventricular tachyarrhythmia (PT)	
	Supraventricular tachycardia (PT)	
	Tachyarrhythmia (PT)	
	Tachycardia (PT)	
	Tachycardia paroxysmal (PT)	
	Ventricular tachyarrhythmia (PT)	
	Ventricular tachycardia (PT)	
	Maximum heart rate increased (PT)	
Hypersensitivity reactions	Hypersensitivity SMQ – Narrow search	
CV - QT prolongation	Torsade de pointes/QT prolongation SMQ – Broad search	

## 5.4.2 Vital Signs

Single blood pressure, pulse and body temperature measurements will be performed at visit 1/screening, visit 2/baseline, visit 3/week 4, visit 4/week 8, visit 5/week 12 (EoT).

Measurements will be per standard clinic practices. Single measurements of blood pressure, pulse, and body temperature will be measured in the sitting position (when possible, otherwise supine, but always in the same position).

Body temperature will be measured with an ear thermometer.

